9.8. Level of significance

The significance level will be 0.05 (5%).

9.9. Subgroup analyses

Subgroup analyses for the primary outcomes may evaluate the treatment effect across the following subgroups: geographic region, duration of symptoms prior to enrolment, age, and

sex. Subgroup analyses might include additional interaction tests to determine whether the effect of treatment varies by subgroup.

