Open multi-centre observational study of efficacy and safety of a medicinal

	
product.
 
The clinical efficacy will be assessed by changes in the patient's clinical status, duration of hospitalization, oxygenation/mechanical ventilation. The clinical examination will include clinical, laboratory, and instrumental investigations according to the current guidelines on treatment of COVID-19 in the Russian Federation.

POPULATION	Hospitalized patients of 18 years and older with confirmed COVID-19.
SAMPLE SIZE	At least 50 patients
TREATMENT ALLOCATION	All study subjects will receive treatment with Polyoxidonium, lyophilizate, 12 mg, in addition to the standard treatment
DIAGNOSIS	Verified COVID-19

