4. STUDY DESIGN

4.1. Primary and Secondary Outcomes

According to the aim and objectives of this study, safety and efficacy of Polyoxidonium®, lyophilizate for solution for injections and topical application, 6 mg (NPO Petrovax Pharm LLC, Russia) will be evaluated in hospitalized patients with coronavirus disease (COVID-19).

Efficacy outcomes

Primary efficacy outcome

Subject clinical status using the WHO 7-point ordinal scale on day 15 as compared to baseline.

1. Not hospitalized, no limitations on activities.
2. Not hospitalized, limitation on activities.
3. Hospitalized, not requiring supplemental oxygen.
4. Hospitalized, requiring supplemental oxygen.
5. Hospitalized, on non-invasive ventilation or high flow oxygen devices.
6. Hospitalized, on invasive mechanical ventilation or ECMO.
7. Death.

Secondary efficacy outcomes

Clinical severity assessed by scales

1. Subject clinical status using the WHO 7-point ordinal scale

- Time to improvement of each parameter of the primary scale from admission.

- Subject clinical status at days 3, 5, 8, 11, and 29.
 - Average change in the clinical status at days 3, 5, 8, 11, 15, and 29 as compared to baseline.
2. *The NEWS Score (National Early Warning Score) describes the vital signs (pulse rate, breathing rate, temperature, blood pressure etc.) and its deviation from the reference ranges):* is evaluated daily and on day 15.
- The time to discharge or to a NEWS of ≤ 2 and maintained for 24 hours, whichever occurs first.
 - Change from baseline to days 3, 5, 8, 11, 15, and 29 in NEWS.
3. *Oxygenation, including mechanical ventilation:*
- Change (day by day) in the need for oxygenation in the first 28 days (up to day 29).
4. *Hospitalization*
- Duration of hospitalization (days).
5. *Mortality (date, cause)*
- 28-day mortality.
6. *SOFA scale (evaluation of organ failure associated with sepsis):* is evaluated daily and on day 15.
- Change from baseline to days 3, 5, 8, 11, 15, and 29 in SOFA.

Safety outcomes

Safety outcomes

- Cumulative incidence of serious adverse events/reactions (SAEs, SARs)
- Cumulative incidence of adverse events/reaction (AEs, ARs)
- Permanent or temporary discontinuation of infusions/injections (by any cause)
- Clinically significant changes in the levels of leukocytes, haemoglobin, platelets, creatinine, glucose, total bilirubin, ALT, AST, CRP, and other parameters.

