Patients who meet the inclusion criteria and do not meet any of the exclusion criteria will be included in a single study group, that will receive Polyoxidonium®, lyophilizate for solution for injections and topical application, 6 mg (NPO Petrovax Pharm LLC, Russia) in dose of 12 mg once daily intravenously (IV) for 3 days, then every other day intramuscularly (IM) on days 5–17 (the total treatment course is 10 injections).

The data collected in this observational program should help doctors find more effective therapy for other patients with COVID-19.

The study will include the following periods:

- **Treatment period** (17 days in total, days 1...17, if the study criteria are met) with administration of the investigational product (IP) (intravenous injections for 3 days, then intramuscular injections for 14 days), assessment of the clinical status, recording of AEs.

- **Follow-up period** (days 18...29±3)

Figure 4.1 shows the study flow chart.

[figure not shown]

Figure 4.1. Study flow chart

¹ MASTER PROTOCOL. A Multi-centre, Adaptive, Randomized, Double-Blind, Placebo-Controlled Clinical Trial of the Safety and Efficacy of Investigational Therapeutics for the Treatment of COVID-19 in Hospitalized Patients. Electronic source Free access: <https://www.who.int/blueprint/priority-diseases/key-action/multicenter-adaptive-RCT-of-investigational-therapeutics-for-COVID-19.pdf>. Access date: March 13, 2020

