4.3.1. Blinding

In contrast to interventional clinical trials, the design of non-interventional trials does not involve randomization and blinding. In accordance with the non-intervention principle, the doctor's decision to prescribe a therapy is made before the patient is included in the study as part of routine clinical practice and in no way can be associated with the possibility of the patient participating in this study. As a result, blinding is impossible. The procedures will be carried out within the current routine clinical practice in the presence of relevant therapeutic indications.

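### The subgroup interaction tests in 9.9 cannot show whether the treatment effect varies, because every patient is treated and prognosis cannot be separated from effect

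*Combined protocol and SAP*

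**What the plan says.** Section 9.9 (Subgroup analyses) opens: "Subgroup analyses for the primary outcomes may evaluate the treatment effect across the following subgroups: geographic region, duration of symptoms prior to enrolment, age, and"; the fourth and last factor listed is sex. It continues: "Subgroup analyses might include additional interaction tests to determine whether the effect of treatment varies by subgroup". It gives no model, outcome form or cut-points.

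The design leaves nothing to cross with these factors. Under section 4.2, eligible patients "will be included in a single study group, that will receive Polyoxidonium". The synopsis says "All study subjects will receive treatment with Polyoxidonium, lyophilizate, 12 mg, in addition to the standard treatment". Section 4.3.1 says "the design of non-interventional trials does not involve randomization and blinding", and 4.3.2 marks randomisation as not applicable. The planned size is "At least 50 patients", with no derivation.

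The outcome appears in two forms. Section 4.1 has "Subject clinical status using the WHO 7-point ordinal scale on day 15 as compared to baseline", while 9.7.2.1 refers to status on Day 15 without the comparison with baseline. Section 9.7.2.1 also plans evaluation by baseline severity, because it expects clinical trajectories to differ with severity at entry.

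**The concern.** An interaction test asks whether the treated-minus-untreated difference changes across subgroups, so it needs treated and untreated patients within each subgroup. Here there are none of the latter. What can be compared is how treated patients fare in one subgroup against another, and that comparison would be expected to show differences even for an inert drug if, say, age or symptom duration relates to recovery.

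The risk is one of interpretation. Section 9.9 describes its p-value as evidence on variation in treatment effect, so a significant result could be reported as the drug working better in one kind of patient. A non-significant one could be reported as a uniform effect. The data could support neither statement. Correcting the between-group wording elsewhere in section 9 would leave this sentence in place.

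**Working it through.** **Inputs from the documents.** One group, all treated (4.2, synopsis); no randomisation (4.3.1, 4.3.2); at least 50 patients (synopsis); significance level 0.05 (9.8; two-sided assumed); factors region, symptom duration, age and sex (9.9). The plan gives no power, effect size or SD, so it has no figure to reproduce.

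**Step 1: what can be estimated.** Let G mark the subgroup and T the treatment. The interaction model is

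E[Y] = a + b·G + c·T + e·T·G.

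With T = 1 for everyone this becomes E[Y] = (a + c) + (b + e)·G. Only the sum b + e is estimable, and e, the quantity of interest, is not. Equivalently, with natural course m and treatment effect d in each subgroup, the observable contrast is

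(m₁ − m₂) + (d₁ − d₂).

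This holds at any sample size and for either form of the outcome.

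**Step 2: consequences for a simple test.** Assumptions not in the documents: 50 patients split 25/25, SD of change 1.5 points, two-sided t-test at 0.05. The standard error is 1.5 × √(2/25) = 0.424. A 1.0-point difference gives 1.0/0.424 = 2.36, and power ≈ Φ(2.36 − 1.96) ≈ 65%. Simulation (20,000 runs) gives:

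| Scenario | Rejects |
|---|---|
| No difference of either kind | 5.1% |
| No drug effect; prognosis differs by 1.0 | 64.6% |
| Same non-zero effect in both; prognosis differs by 1.0 | 63.5% |
| Effect differs by 1.0; prognosis equal | 63.8% |
| Effect differs by 1.0; prognosis half offsets it | 20.9% |
| Effect differs by 1.0; prognosis fully offsets it | 5.0% |

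Rows two to four cannot be told apart in the data, and neither can the first and last. For a pure prognosis difference of 1.0 point the rejection rate runs from 42% (SD 2.0) to 94% (SD 1.0). At SD 1.5 it is 22% for 0.5 points and 94% for 1.5 points.

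**Step 3: the same point on the ordinal scale.** Assumptions: 25 vs 25, same baseline mix, zero drug effect, recovered patients reach category 1 and the others stay at baseline, Mann-Whitney on change, 4,000 runs. Recovery of 90% against 70%, 60% or 50% rejects about 25%, 50% or 75% of the time. Identical subgroups reject about 5%.

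**Step 4: baseline mix alone, zero drug effect.** Take mixes for categories 3/4/5/6 of 60/30/10/0% against 20/40/30/10%.
- If 80% of patients in each subgroup recover straight to category 1, change rejects about 51%.
- If improvement is stepwise, change rejects about 5%, but Day 15 status rejects about 54%.

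A milder pair of mixes (50/35/15/0% against 35/35/25/5%) gives about 14% on change under the first law, and about 15% on status under the stepwise law. The direction also depends on the outcome. On change under the first law, the sicker subgroup appears to gain more; on status, it looks worse. No single figure represents this route.

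**Step 5: what the missing comparator would supply.** With an assumed concurrent untreated group (1:1, SD 1.5), a true interaction test with a 1.0-point prognosis difference and no modification rejects 4.9%, 4.7% and 4.9% at N = 48, 200 and 400. With 1.0 point of modification and the same offsetting prognosis, its power is 21%, 65% and 91%. The defect is therefore the absent comparator, and more treated patients would not cure it.

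**The case against.** Section 9.9 is permissive throughout: it says the analyses may be done and might include tests. It fixes no model, cut-point or decision rule, and 4.3 acknowledges the usual limitations of an observational study. This stands as a limit on severity, but an optional test is no more valid when it is run.

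The problem also shares its root with other wording that has no second group behind it: patients of both groups in 2.4.2, a comparator in 2.5, and treatment groups in 9.7.2.2 and 9.7.3. That is fair, but repairing those places would not remove the effect-modification sentence here.

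A reader might infer several stronger things that the documents do not support:
- That the test always rejects falsely and always misses real modification. Both are conditional on prognosis. With equal prognosis the test does respond to modification, though nothing in the data shows that this case applies.
- That change from baseline is the only outcome that could be tested, so that a subgroup sicker at entry must show a larger apparent effect. Section 9.7.2.1 uses status on Day 15, and step 4 shows that both the size and the direction depend on the outcome and the assumed recovery pattern.
- That 9.9 tests sicker against milder patients. Severity is not among its factors and is handled in 9.7.2.1.
- That the plan will use these results to decide who receives the drug. Section 4.2 speaks only of helping doctors find more effective therapy in general.

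**Conclusion.** The point holds as a structural one: treatment-by-subgroup variation is not estimable in this design, and any subgroup p-value mixes prognosis with effect. That conclusion rests only on the single treated group without a comparator, and needs none of the assumed numbers.

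The size of the error depends on how far prognosis differs between subgroups, which the documents do not give. Under the assumed recovery rates in step 3, rejection is about 25% to 75% in place of 5% with no drug effect. From baseline mix alone it ranges from about 5% to 50% or more, depending on the outcome and the recovery pattern. Section 9.9 is wrong as written, but the remedy is a change of wording and not of design. The same limit applies to the baseline-severity analysis in 9.7.2.1 if its results are read as treatment effects.

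**What to change.** - In 9.9, replace the phrase about evaluating the treatment effect across subgroups with one that describes Day 15 WHO status and change from baseline across the same four factors.
- Delete the sentence on interaction tests.
- Add a statement that subgroup differences are prognostic associations and not variation in treatment effect.
- Apply the same label to the baseline-severity analysis in 9.7.2.1.

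A baseline-adjusted estimate with a 95% confidence interval for each factor is an optional extra. With about 50 patients, sparse categories may have to be collapsed, so it should not be a requirement.

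The change needs no new data, visits or patients. Its only cost is giving up a claim that the design cannot support.

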9.10. Procedures that increase accuracy of the statistical analysis

Monitors will check the case report forms for missing data during monitoring visits to the centre. If any data are absent in the CRF and are present in the source records, relevant inquiries and instructions for the corrective actions will be sent to the study doctors.

The statistician and the Principal Investigator will review the database for any doubtful, missing, and non-analysable data. Inquiries will be sent to the investigators in case of any findings.

If necessary, the study doctors will correct the errors in CRFs and inform the Principal Investigator and the monitors about the corrective actions. If the identified errors in the data cannot be corrected after the completion of the subjects' participation in the study, sensitivity of the resulting parameters to questionable data will be performed as part of the statistical analysis. Information about any missing, doubtful, and non-analysable data will be presented in the Clinical Study Report.

10. DIRECT ACCESS TO THE SOURCE DATA/SOURCE RECORDS

Source data is the information contained in the original medical records and their certified copies that describe the results of clinical observations, examinations and other activities and allow reproducing the course of a clinical study and evaluate its quality. Source data is entered to the source records (originals or their certified copies) and to electronic form if an electronic data collection system is used.

The study doctor has to authorize monitoring of the study (by the authorized representative of the Sponsor), audits (by the authorized representative of the Sponsor or the company authorized by the Sponsor to conduct audits of the study centre) and inspections by the regulatory authorities with direct access to source data and source records.

11. QUALITY CONTROL AND ASSURANCE

11.1. General information on quality assurance and quality control

The sponsor must provide an appropriate quality assurance and quality control system for the conduct of this clinical study in accordance with the Study Protocol, Good Clinical Practice, and other regulatory requirements that are applicable to non-interventional studies.

The study doctor and members of the study team must strictly follow the study procedures specified in the Protocol.

11.2. Risk management

The methods used to ensure and control the quality of the study should be correlated with the risks inherent to all parts of the observational study and importance of the data obtained during the study. The quality management system should use a risk-based approach.

In accordance with the FDA Guidance on Conduct of Clinical Trials of Medical Products during COVID-19 Public Health Emergency¹, the study procedures will be conducted with respect for the rights of the subjects, ensuring their security, as well as taking into account national and international regulatory requirements for managing and controlling the spreading of COVID-19, including quarantine measures.

The Sponsor is responsible for composing the risk management plan for the clinical study. The risk management plan is part of the clinical study project.

11.3. Clinical study monitor

Sponsor or the designated vendor will monitor the clinical study to:

- ensure protection of the rights and health of the patients,
- review the accuracy and reliability of the data entered in the CRFs and the source records,
- verify that the study doctor and members of the study team follow the procedures of the approved study Protocol, current amendments to the protocol (if applicable), Good Clinical Practice, and applicable regulatory requirements.

Clinical study monitoring is carried out according to the approved plan. Monitor must comply with the written standard operating procedures of the Sponsor/CRO, as well as procedures that were specified by the Sponsor/CRO to monitor this study.

The monitor must ensure that the study is conducted and documented properly. Monitor has the following duties and responsibilities:

- acts as the main link between the Sponsor and the study doctor,
- verifies that the Investigator has the required qualification and sufficient resources, including laboratories, equipment, and personnel throughout the study,
- controls the investigational product (storage terms, shelf life, a sufficient stock of the product in the centre, the correct administration of the investigational product, the accounting),
- verifies that the study doctor complies with the approved Protocol and all approved Amendments to the protocol (if applicable),
- verifies that the Patient Information Sheet and the informed consent form for participation in the clinical study is signed in a timely manner, i.e. before the patient is included in the study,
- ensures that the study doctor has the current version of the study records (protocol, amendments to the protocol (if applicable), investigator's brochure, patient information leaflet and informed consent form for participation in the clinical study),

¹ FDA Guidance on Conduct of Clinical Trials of Medical Products during COVID-19 Public Health Emergency. Electronic source. Free access: <https://www.fda.gov/media/136238/download>. Access date: March 20, 2020.

- provides sufficient information about the study to the study doctor and the study team,
- controls how the study doctor and study team fulfil their duties within the study in accordance with the protocol and other applicable agreements/contracts between the Sponsor and the study doctor/healthcare institution,
- verifies that the study team fulfils their duties independently (that the study doctor duties are not transferred to unauthorized persons),
- monitors how the study doctor complies with the eligibility criteria,
- informs the Sponsor about the enrolment rate,
- verifies the accuracy and completeness of data in the CRF, source records and other study records by comparing them,
- informs the study doctor about any errors, omissions, and illegible entries in the CRF,
- verifies compliance with the adverse events reporting deadlines defined by this Protocol,
- verifies filing of the main study documents by the study doctor,
- informs the study doctor of deviations from the Protocol, SOP, regulatory requirements, and takes the necessary actions to prevent the recurrence of such deviations.

11.4. Audit by Sponsor

The Sponsor's audit is carried out separately and independently of the routine monitoring and quality control of the clinical study. The purpose of the audit is to assess the conformity of the study to the protocol, SOPs, and regulatory requirements.

For the audit, the Sponsor appoints individuals who are not involved in this clinical trial.

The sponsor must make sure that the auditors are qualified to conduct the audit properly. The qualifications of the auditor must be documented.

The sponsor or the designated vendor develop an audit plan and audit procedures for this study.

11.5. Actions of the Sponsor in response to non-compliance with applicable requirements

The Sponsor should take immediate actions in case of any non-compliance with the Protocol, SOPs, and/or related regulatory requirements by the study doctor/study centre, CRO or Sponsor's staff.

If any serious and/or repeated non-compliance with applicable requirements by the study doctor/health care institution/CRO are detected during monitoring or audit, the Sponsor may terminate the participation of the violating party in the study. If participation of the investigator/study centre in the study is terminated because of serious or repeated non-compliance with the applicable requirements, the Sponsor must notify the regulatory authorities.

11.6. Clinical Study Documents

The Sponsor provides the following main documents and materials to the study centre:

- study protocol (with amendments, if any),
- Investigator's Brochure,
- patient information sheet with informed consent form for participation in the observational study,
- investigational product (IP),
- agreement,
- documents required for submission to the local ethics committee.

The study doctor provides the Sponsor with the following key documents before the start of the study:

- a referral letter to the local ethics committee (if any),

- signed confidentiality agreement,
- signed investigator statement of agreement with the protocol,
- approval of the protocol by the local ethics committee,
- list of members of the local ethics committee,
- CVs of all study doctors (signed and dated),
- laboratory reference ranges with the signature and date of the responsible laboratory employee,
- certificates for medical / laboratory equipment.

The study doctor must keep clinical study documents (source records and the investigator file) for 15 years after the completion of the study.

11.7. Amendments to the protocol

Amendment to the Protocol is a written description of the changes or a message about the amendments, or an official explanation of the Protocol.

Amendments to the Protocol are significant if changes to the Protocol affect the safety or physical/mental well-being of the patients, the scientific value of the study, the study procedures, the quality or safety of the investigational product, or if it implies replacement of the responsible study doctor in the centre or inclusion of a new centre in the study.

Any changes or additions to this Protocol require should be issued as written amendments to the protocol and approved before entry into force.

Any changes or additions to this Protocol require should be issued as written amendments to the protocol and approved before entry into force.

Any amendments which affect the safety of patients, conduct or the scientific value of the study should be further approved by the local ethics committee.

Changes to the Protocol that affect only the administrative aspects of the study do not require the approval of the local ethics committee, but the parties should be notified of such amendments in writing.

The final study report should describe frequency and type of Protocol Amendments and explain how the changes affect results of the study.

